**6.4 SAFETY POPULATION**

The Safety Population will consist of all participants in the Randomized Population who receive at least 1 dose of double-blind study intervention.

Participants will be summarized according to the study intervention they actually receive for all safety analyses. If a participant received study intervention different from the randomized study intervention, actual study intervention received will be determined based on the study intervention received for majority of the double-blind Study Intervention Period. If there is a tie, higher dose will be considered for actual study intervention for that participant. Actual study intervention will be listed for the participants in the listing related to study intervention dosing information.

**7.0 PARTICIPANT DISPOSITION**

The disposition summaries will be provided by study intervention group for each cohort separately (as appropriate for double-blind Study Intervention Period and Postintervention Period). If any cohort has linaclotide dose similar to the other cohort, summary statistics will also be provided by combining the participants from similar dose cohorts. Summaries will also be provided for participants from all cohorts in the placebo group.

The number and percentage of participants in 3 study populations (Randomized, mITT, and Safety) will be summarized overall, by study intervention group, country, and study center within the corresponding cohort; the number of participants screened will be summarized overall, only by country, and study center.

Screen-failure participants (ie, participants who are screened but do not enter into the Preintervention Period), participants ineligible for randomization (ie, participants who enter into the Preintervention Period but are not randomized at Visit 3, also labeled as preintervention failures), and the associated reasons for failure as recorded in the electronic case report forms (eCRF) will be tabulated overall for all the screened participants.

The number and percentage of participants who complete the study, complete the double-blind Study Intervention Period, complete the Postintervention Period, prematurely discontinue the study, prematurely discontinue the double-blind Study Intervention Period, and prematurely discontinue the Postintervention Period will be presented for each study intervention group and pooled across study intervention groups for the Randomized Population within the corresponding cohort. The reasons for premature discontinuation from the study and from the corresponding period as recorded in the eCRF will be summarized (number and percentage) by study intervention group for the Randomized Population within each cohort. All participants who prematurely discontinue during the Study Intervention Period or Postintervention period will be listed by discontinuation reason for the Randomized Population for all the cohorts.

## **8.0 DEMOGRAPHICS AND OTHER BASELINE CHARACTERISTICS**

The demographic, baseline characteristics, medical and surgical histories, prior and concomitant medications, and significant protocol deviations will be summarized by study intervention group for each cohort separately. If any cohort has linaclotide dose similar to the other cohort, summary statistics will also be provided by combining the participants from similar dose cohorts. Summaries will also be provided for participants from all cohorts in the placebo group.

Demographic parameters (age; race; ethnicity; sex) and baseline characteristics (weight; height; and body mass index, calculated as weight [kg]/(height [m])) will be summarized descriptively by study intervention group for the mITT and Safety Populations.

Other baseline characteristics (including efficacy parameters related to the bowel habits and symptoms as discussed in Section 10.0) will be summarized descriptively by study intervention group for the mITT Population.

Continuous variables will be summarized by number of participants, mean, standard deviation (SD), median, minimum, and maximum values. Categorical variables will be summarized by number and percentage of participants.

Abnormalities in participants' medical and surgical histories will be coded using the Medical Dictionary for Regulatory Activities, version 23.0 or newer. The number and percentage of participants with abnormalities in medical and surgical histories in each system organ class and preferred term will be summarized by study intervention group for the Safety Population.

*Prior medication* is defined as any medication taken before the date of the first dose of study intervention. *Concomitant medication* is defined as any medication taken on or after the date of the first dose of study intervention. Any prior medications stopped more than 30 days before the date of the first dose of study intervention and any concomitant medications started after the date of the last dose of study intervention will not be presented in the summary tables but will be included in the participant data listings.

Both prior and concomitant medications will be coded by drug name and therapeutic class. The use of prior and concomitant medications will be summarized by the number and percentage of participants in each study intervention group for the Safety Population. If a participant took a specific medication multiple times or took multiple medications within a specific therapeutic class, that participant would be counted only once for the coded drug name or therapeutic class.

The World Health Organization (WHO) Drug Dictionary, version B2 Enhanced 201703 or newer, will be used to classify prior and concomitant medications by therapeutic class and drug name.

Unique participants reporting significant protocol deviations will be summarized by study intervention group for the Randomized Population.

**9.0 EXTENT OF EXPOSURE AND STUDY INTERVENTION COMPLIANCE**

The summary statistics will be provided by study intervention group for each cohort separately. If any cohort has linaclotide dose similar to the other cohort, summary statistics will also be provided by combining the participants from similar dose cohorts. Summaries will also be provided for participants from all cohorts in the placebo group.

**9.1 EXTENT OF EXPOSURE**

Exposure to the study intervention for the Safety Population during the double-blind Study Intervention Period will be summarized for study intervention duration, calculated as the number of days from the date of the first dose of study intervention to the date of the last dose of study intervention, inclusive. Descriptive statistics (number of participants, mean, SD, median, minimum, and maximum) will be presented by study intervention group.

*Participant-years*, defined as exposure to the study intervention in years, will be summarized by study intervention for the Safety Population.

**9.2 MEASUREMENT OF STUDY INTERVENTION COMPLIANCE**

Dosing compliance for the double-blind Intervention Period is defined as number of capsules actually taken by a participant during that period divided by the number of capsules prescribed for that period multiplied by 100. This information will be obtained from the study intervention record of the participant's eCRF. The capsule contents are to be sprinkled into 20 mL of bottled water, and 5 mL of this solution is dosed to the participant using an oral syringe as instructed in protocol Appendix 7 ([Section 10.7](#) in protocol).

The number of capsules expected to be taken for the double-blind Intervention Period will be calculated by multiplying the number of days in that period by the number of capsules to be taken per day. Descriptive statistics for study intervention compliance will be presented by study intervention group between 2 consecutive visits, as well as for the whole double-blind Intervention Period for the Safety Population.

**9.3 EDIARY COMPLIANCE**

An observer-reported outcome (ObsRO) instrument assessing key signs and symptoms of FC for use in children (2 to 5 years of age) with FC was developed for completion by caregivers on the electronic diary (eDiary) daily. eDiary compliance will be assessed based on the number of days with fully completed daily eDiary assessments by the caregiver in a specific period. eDiary will be considered fully completed if the caregiver responded to each question in the daily eDiary. eDiary compliance will be summarized for the Preintervention Period, double-blind Intervention Period, Postintervention Period, and for each week within each period based on the mITT Population.

Compliance for each participant/interval will be calculated using the following formula:

$$\text{%Compliance} = \frac{100 * \text{# of days with completed eDiary entries within the interval}}{\text{# of expected days within the interval}}$$

On randomization day, the diary administered before the randomization time will be included in Preintervention Period.

## **10.0            EFFICACY ANALYSES**

The efficacy analyses will be based on the mITT Population.

Baseline values for efficacy endpoints related to daily eDiary responses will be derived from the eDiary in the Preintervention Period, specifically the time period from 14 days before randomization up to the time of randomization.

A SBM is a BM that occurs in the absence of laxative, suppository, or enema use on the calendar day of the BM or the calendar day before the BM. Caregiver-observed SBMs are defined as SBMs reported in the eDiary for which the caregiver identified being with the child for.

Baseline SBM weekly rates, stool consistency for caregiver-observed SBMs, and straining for caregiver-observed SBMs will be derived as discussed in Section 16.3 from 14 days prior to randomization and up to the time of randomization. A participant's baseline stool consistency and straining reported for caregiver-observed SBMs cannot be assessed if the participant does not have at least 1 caregiver-observed SBM during the Preintervention Period. For participants with no caregiver-observed SBMs reported in the eDiary during a study period, the consistency and straining assessments reported by caregiver will be considered missing for that study period in the analyses. Participants with missing baseline consistency and straining reported by the caregiver will be excluded from the respective consistency and straining change from baseline analyses.

Baseline value for the global severity in symptoms will be based on the last non-missing assessment on or before the date of first dose of study intervention.

An observed-cases approach to missing postbaseline data will be applied. Efficacy analyses will be performed via descriptive summary statistics in terms of mean, median, SD, standard error of mean, minimum, and maximum. No statistical testing will be performed to compare linaclotide dose with placebo. No multiplicity adjustment will be applied in this dose-ranging study.

### **10.1        KEY EFFICACY ENDPOINTS**

There are 4 key efficacy endpoints in this study.

- Change from Baseline in 4-Week Overall SBM Frequency Rate (SBMs/week) During the Study Intervention Period of Each Cohort**

The SBM rate per week during the Study Intervention Period will be derived based on the total number of SBMs reported by a caregiver as being directly observed by the caregiver during this period in the eDiary, as discussed in Section 16.3.4.

Descriptive statistics (mean, median, SD, standard error of mean, minimum, and maximum) will be provided by study intervention group for each cohort as main analysis approach. The sensitivity descriptive statistics will also be provided by first imputing the postbaseline missing daily data during Study Intervention Period with the worst response for caregiver-observed SBM (i.e. assuming 'Yes' response for missing rescue medication use).

Descriptive summary statistics similar to main analysis approach will be provided for change from baseline in 4-week overall SBM frequency rate including the SBMs not directly observed by the caregiver.

- **Change from Baseline in 4-Week Stool Consistency Reported by the Caregiver During the Study Intervention Period of Each Cohort**

Stool consistency for caregiver-observed SBMs will be derived as discussed in Section 16.3.5. Descriptive statistics (mean, median, SD, standard error of mean, minimum, and maximum) will be provided by study intervention group for each cohort.

- **Change from Baseline in 4-Week Straining Reported by the Caregiver During Study Intervention Period for Each Cohort**

Straining for caregiver-observed SBMs will be derived as discussed in Section 16.3.6. The summary statistics for this key efficacy endpoint will be provided by study intervention group in the similar way as discussed for change from baseline in 4-week stool consistency reported by the caregiver during Study Intervention Period for each cohort.

- **Proportion of Days With Fecal Incontinence During Study Intervention Period (For Participants Who Have Acquired Toileting Skills During Daytime and Nighttime or Acquired Toileting Skills During Daytime Only) Within Each Cohort**

The presence of fecal incontinence in a day will be determined as discussed in Section 16.3.7. The proportion of days with fecal incontinence during the Study Intervention Period will be derived based on number of non-missing diary reported days with fecal incontinence responses during the Study Intervention Period in the denominator. Descriptive statistics (mean, median, SD, standard error of mean, minimum, and maximum) by study intervention group will be provided within each cohort.

In the analysis of any key efficacy endpoint, if any cohort has linaclotide dose similar to the other cohort, descriptive summary statistics will also be provided by combining the participants from the similar dose cohorts. In addition, the summary statistics will also be provided for placebo group by combining placebo participants from all cohorts.

Cumulative distribution function plots will be provided for the key efficacy endpoints related to change from baseline by study intervention group. Weekly descriptive summary of the change from baseline key efficacy endpoints will be provided by study intervention group.

## 10.2 OTHER EFFICACY ENDPOINTS

The other efficacy endpoints are discussed below:

- Proportion of participants with each individual item score for the global change in child's constipation and the global severity of child's constipation at each week during the double-blind Study Intervention Period.

The details of these global items are discussed in Section 16.3.8. Counts and percentages will be provided by study intervention group for each category of global change in child's constipation [REDACTED] and global severity of child's constipation [REDACTED] at each week during the Study Intervention Period for each cohort.

- **Proportion of participants who no longer fulfill modified Rome III criteria for functional constipation at the end of the study intervention period**

Modified Rome III criteria will be assessed by the investigator at the Screening Visit (Visit 1) and at the end of the study intervention period at the EOT Visit (Visit 5). A participant will be considered as fulfilling modified Rome III criteria if a "yes" response is recorded to the overall question of whether the participant meets modified Rome III criteria for functional constipation. For the EOT assessment, these criteria will be assessed over the 4-week double-blind study intervention period. In the event a participant discontinues the study prematurely, these criteria will be assessed over the duration of time the participant received double-blind study intervention. Counts and percentages will be provided by study intervention group for participants no longer fulfilling modified ROME III criteria at the end of the study intervention period for each cohort.

If any cohort has linaclotide dose similar to the other cohort, summaries for other efficacy endpoints will also be provided combining the participants from similar dose cohorts. The summary statistics will also be provided for placebo group combining placebo participants from all cohorts.

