- The participant must complete at least 4 weeks (28 days) of study intervention before returning for Visit 5 (Week 4). The last dose of study intervention will be administered at the study site at the Visit 5 (Week 4) visit on Day 29 (+2) at approximately the same time as on other days of study intervention administration. Caregivers will be instructed when the participants should fast to ensure they have fasted for at least 2 hours before receiving their last dose of study intervention (Section 10.8.3)
- All randomized participants who prematurely discontinue from the study, regardless of cause, are required to be seen for the assessments completed at EOT (Visit 5, Week 4), except for PK sample collection.
- The parent/guardian/legally authorized representative must provide written informed consent before the participant's enrollment in the study. If a parent or legal guardian is also the participant's caregiver, he or she will be asked to sign a combined parent and caregiver written informed consent. Caregivers other than parent or legal guardian must provide written informed consent.
- Prior to dosing, the investigator or appropriate site staff member will assess if Rome IV criteria for Child FC was met and record the outcome in the eCRF. Eligibility for the study is not based on this assessment.
- Participants in Cohorts 1-3 will be randomized on Study Day 1 (Visit 3) at a 1:3 ratio to either a predose or postdose PK sample respectively. The 6 additional participants in the final cohort will be randomized at a 1:2 ratio to either a pre-dose or post-dose PK sample, respectively (Section 8.5.1).
- Physical examinations will be performed by medically qualified site personnel at Screening (Visit 1) and Week 4 (Visit 5) and may be repeated at the investigator's discretion. If fecal impaction (as defined in footnote h below) is documented during an optional repeat physical examination, the study physician must be notified.

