5.1. Inclusion Criteria

The targeted participant population will include male and female participants, 2 to 5 years of age. Participants are eligible to be included in the study only if all of the following criteria apply:

1.	Age and Weight
1.01	Male and female participants must be ages 2 to 5 years, (inclusive) at the time the parent/guardian/LAR has provided signed consent
1.02	Participant weighs $\geq 10~kg$ at the time the parent/guardian/LAR has provided signed consent
2.	Type of Participant and Disease Characteristics

2.01	Participant meets modified Rome III criteria for FC: For at least 2 months before Screening (Visit 1) (for participants aged ≥ 4 years old), or for at least 1 month before Screening (Visit 1) (for participants aged < 4 years old), the participant has had 2 or fewer defecations (with each defecation occurring in the absence of any laxative, suppository, or enema use during the preceding 24 hours) per week.		
	In addition, at least once per week, participant must meet 1 or more of the following:		
	a. History of retentive posturing or excessive volitional stool retention		
	b. History of painful or hard bowel movements (BMs)		
	c. Presence of a large fecal mass in the rectum		
	d. History of large diameter stools that may obstruct the toilet		
	e. At least one episode of fecal incontinence per week after the acquisition of toileting skills		
2.02	Participant is willing to discontinue any laxatives used before the Preintervention Visit in favor of the protocol- permitted rescue medicine.		
2.03	Participant has an average of fewer than 3 SBMs per week during the 14 days before the randomization day and up to the randomization (including the clinic eDiary assessments reported before administration of first dose of double-blind study intervention on the randomization day). An SBM is defined as a BM that occurs in the absence of laxative, enema, or suppository use on the calendar day of the BM or the calendar day before the BM		
2.04	Caregiver is compliant with eDiary requirements by completing daily assessments for 10 out of the 14 days immediately preceding the Randomization Visit.		
3.	Informed Consent		
3.01	Parent/guardian/LAR and caregiver must provide written informed consent before the initiation of any study-specific procedures		
3.02	Caregiver who will be completing the eDiary is able to read and/or understand the assessments in the eDiary device and must undergo training		

CONFIDENTIAL

linaclotide

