9.1. Statistical Endpoints

Key efficacy endpoints include:

- Change from baseline in 4-week overall SBM frequency rate (SBMs/week) during the Study Intervention Period of each cohort
- Change from baseline in 4-week stool consistency reported by the caregiver during the Study Intervention Period of each cohort
- Change from baseline in 4-week straining reported by the caregiver during the Study Intervention Period of each cohort

 Proportion of days with fecal incontinence during the Study Intervention Period (for participants who have acquired toileting skills during daytime and nighttime or acquired toileting skills during daytime only) within each cohort

Other efficacy endpoints include:

- Proportion of participants who no longer fulfill modified Rome III criteria for functional constipation at the end of the Study Intervention Period.
- Proportion of participants with each individual item score for the global change in symptoms and the global severity of symptoms at each week during the Study Intervention Period.

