9.4.1.2. Other Efficacy Endpoints

Proportion of participants who no longer fulfill modified Rome III criteria for functional constipation at the end of the study intervention period

Modified Rome III criteria will be assessed by the investigator at the Screening Visit (Visit 1) and at the end of the study intervention period at the EOT Visit (Visit 5). A participant will be considered as fulfilling modified Rome III criteria if a "yes" response is recorded to the overall question of whether the participant meets modified Rome III criteria for functional constipation. For the EOT assessment, these criteria will be assessed over the 4-week double-blind study intervention period. In the event a participant discontinues the study prematurely, these criteria will be assessed over the duration of time the participant received double-blind study intervention (Section 8.1.2).

Proportion of participants with each individual item score for the global change in symptoms and the global severity of symptoms at each week during the study intervention period

The global change in symptoms and the global severity of symptoms will be assessed on a weekly basis in the eDiary with a 7-point scale and a 5-point scale respectively as discussed in Section 8.1.2.

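### An early discontinuer is judged on weekly modified Rome III criteria over only the days dosed, with no minimum window, so can be counted as no longer fulfilling them

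*SAP*

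**What the plan says.** The endpoint is listed in Protocol Section 9.1 as "Proportion of participants who no longer fulfill modified Rome III criteria for functional constipation at the end of the Study Intervention Period". Protocol Sections 8.1.2 and 9.4.1.2 and SAP Section 10.2 give the same assessment rule. The outcome is the investigator's answer to one overall question on whether the child meets the criteria. For children who reach Week 4, "For the EOT assessment, these criteria will be assessed over the 4-week double-blind study intervention period". For those who discontinue the study early, "these criteria will be assessed over the duration of time the participant received double-blind study intervention".

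The criteria come from inclusion criterion 2.01 (Protocol Section 5.1). The frequency part is that "the participant has had 2 or fewer defecations" per week, not counting those within 24 hours of a laxative, suppository or enema. The second part reads "In addition, at least once per week, participant must meet 1 or more of the following", followed by a list of five features. At entry the look-back is at least 1 month (under 4 years of age) or at least 2 months (4 years and over).

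Early discontinuers "are required to be seen for the assessments completed at EOT (Visit 5, Week 4), except for PK sample collection", so a Rome III answer is due from them. The endpoint is summarized by counts and percentages within each cohort, with similar-dose cohorts also combined and placebo also pooled across cohorts.

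**The concern.** The criteria describe a weekly pattern, and the shortened window can be less than a week. The documents do not say how a per-week threshold applies to, say, 3 days, and set no shortest exposure below which the answer is not assessable. Stool form plays no part in the frequency criterion, so loose stools count as defecations.

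A child who stops because of loose stools can thus exceed two defecations during the days dosed and be recorded as not meeting the criteria. A tolerability problem would then appear in the table as a favourable efficacy result. The trial does no testing, and SAP Section 14.0 says its size is meant to let response trends be observed. Readers will look at the raw percentages, and in arms this small a single child changes them visibly.

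**Working it through.** **1. Can such a child reach the numerator?** Four provisions, taken together, allow it.
- The mITT population requires one dose and one postbaseline bowel movement or rescue entry (SAP Section 6.3), with no minimum exposure.
- The child is due for the EOT assessments, including modified Rome III (Protocol Section 1.3).
- The observed-cases approach (SAP Section 10.0) deals with missing data. Here the answer is recorded, so that approach does not alter it.
- SAP Section 10.1 gives the SBM rate a worst-response sensitivity summary. SAP Section 10.2 gives this endpoint none.

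**2. What does a short window do to the frequency criterion?** Illustration with assumed counts: 3 loose stools in 3 dosed days scale to 3 × 7/3 = 7 per week, and 6 scale to 14 per week. Both exceed 2 per week, and the raw counts also exceed 2. Failing the frequency part is enough for the criteria as a whole not to be met.

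Short windows are unstable even without diarrhea. Assume a Poisson stool count with true weekly rate r over d days, so the mean is r × d/7. Over 3 days, one stool already scales to 7/3 = 2.3 per week, so P(scaled rate > 2) = 1 − exp(−3r/7). Over 28 days the count must be at least 9.

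| True rate per week | 3 days, scaled rate > 2 | 3 days, raw count > 2 | 28 days, scaled rate > 2 |
|---|---|---|---|
| 1 | 35% | 1% | 2% |
| 1.5 | 47% | 3% | 15% |
| 2 | 58% | 6% | 41% |

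A child whose true rate is still in the constipated range would often fail the criterion over 3 days if the count is scaled, and rarely if it is not. The plan does not say which reading applies.

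**3. How much does one child weigh?** The plan's own total reproduces: 3 × 8 + 6 = 30. Allocation of 3:1 in 8 gives 6 linaclotide and 2 placebo; 5:1 in 6 gives 5 and 1.
- One linaclotide arm in Cohorts 1 to 3: 1/6 = 16.7 points (for example, 3/6 = 50.0% against 2/6 = 33.3%).
- Cohort 3 plus the final cohort at the same dose: 1/(6 + 5) = 1/11 = 9.1 points.

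**4. How likely is it?** Protocol Section 2.2.2 reports one discontinuation for related diarrhea in each earlier pediatric study. Linaclotide numbers are 116 + 16 = 132 in LIN-MD-62 and 74 + 8 = 82 in LIN-MD-63, which sum to the 214 stated there. If 2/214 = 0.93% carried over to ages 2 to 5 (an assumption), the chance of at least one such child is 1 − (1 − 2/214)^n: 5.5% for n = 6, 9.8% for n = 11, and 19.4% for all 3 × 6 + 5 = 23 linaclotide children. Using LIN-MD-62 alone (1/132), these are 4.5%, 8.0% and 16.0%.

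**The case against.** The strongest reply is that nothing in the plan forces a favourable score. No stool-count algorithm exists; the outcome is the investigator's overall judgment, and an investigator may well answer that a child seen for 3 days still meets the criteria. A brief bout of diarrhea need not end participation either: Protocol Sections 6.1.1 and 6.6 allow a pause in dosing of up to 3 days, and discontinuation is mandatory for related AESIs and SAEs, not for diarrhea as such (Section 7.1.1). All of this stands. It limits the point to what can happen, without closing the gap, because the investigator is given no rule for a short window.

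A reader might also infer that the dose trend in this endpoint is biased upward. The documents do not support that. The two earlier discontinuations were at Dose C in one study and at Dose B, not the highest dose, in the other. Both were at ages 12 to 17, and no adverse events led to discontinuation in the younger age groups. Their timing is not given. Two events show no gradient. Nor do they exclude one at ages 2 to 5, where Cohort 3 allows up to 7.2 µg/kg against a highest tested 2 µg/kg at ages 6 to 11 (Protocol Section 4.3).

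It can further be said that SAP Sections 7.0 and 11.1 already display discontinuation reasons and adverse events leading to discontinuation, so a careful reader could find such a child. That is true, but the reader would have to link separate displays to reinterpret one percentage.

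Finally, counting every early discontinuer as still fulfilling the criteria would mislabel a child withdrawn late for an unrelated reason after real improvement. In a 2-child placebo arm that is 1/2 = 50 points. This is a sound reason not to make such a count the main result.

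**Conclusion.** The point holds as a cheap improvement. The rule applies weekly criteria to an exposure of any length, and an early discontinuer can be counted as favourable on that basis. If it happens, the effect is 16.7 points in an arm of 6 and 9.1 points in a pooled group of 11. On the rates seen in older children it is unlikely in any one arm (about 5%), though less remote across all linaclotide children (16% to 19%). Those chances assume that the earlier rates carry over, and cover only stopping for diarrhea; the documents give no overall discontinuation rate. The endpoint is descriptive, and dose escalation rests on safety data, so no main conclusion of the trial depends on it.

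The documents do not support reading the rule as automatically turning diarrhea into success, or as producing a known bias across doses. The rule is also worded for a child who discontinues the study; one who stops study intervention but remains in the study is not separately covered.

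**What to change.** Keep the as-assessed row exactly as planned. Before unblinding, add one sentence to SAP Section 10.2 and one row to the same table. In that row, every mITT participant who discontinues before completing the 4-week Study Intervention Period is counted as still fulfilling modified Rome III, whatever answer was recorded. Show the number of such participants for each group and cohort, and the denominator of each row, since a discontinuer with no EOT answer drops out of the as-assessed row but belongs in the added one.

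This parallels the worst-response summary already planned for the SBM rate. It changes no visit, dose or data collection, and it leaves the protocol's analysis in place because the row is additional. The cost is the sentence and the row. The downside is that the added row is conservative for children who stop for unrelated reasons. With the two rows side by side, the reader sees how far the result depends on early discontinuers.
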